	Febrile neutropenia (ANC <1000/mm ³ with temperature of >38.5°C)	Hold until recovery to ANC>1000/mm ³ . Resume at one dose level below current dose level	Hold until recovery to ANC>1000/mm ³ . Resume at same dose level
	Anemia	No reduction or delay	No reduction of delay
Hepatic toxicity	Grade 4 AST, ALT or Total Bilirubin Child Pugh Score	For patients with known liver dysfunction and Child Pugh score A, Eribulin should be started at a dose of 1.1mg/m ² . For patients with known liver dysfunction and Child Pugh score B, Eribulin should be started at a dose of 0.7mg/m ² . Eribulin should not be administered in patients with Child Pugh score C. If during treatment there is grade 3,4 liver toxicity then dose reduce by 1 dose level.	Hold until recovery to Grade 1 or baseline. Resume at reduced dose of 20 mg po daily if first occurrence, reduce to 14 mg po daily on second occurrence and 10 mg po daily on third occurrence.

Peripheral neuropathy	Grade 3 or 4	Hold until recover to \leq grade 2. Reduce dose by one dose level. If neuropathy fails to recover to grade 2 within 3 weeks, Eribulin should be discontinued.	No modifications necessary
Non-hematologic toxicity grade 3 or 4 attributed to any or all treatment (except for neuropathy)	Grade 3 or 4 nausea/vomiting despite optimal antiemetic treatment	Hold until nausea/vomiting have resolved to \leq grade 1. Resume at same dose level	Hold until nausea/vomiting have resolved to \leq grade 1. Resume at same dose.
	>Grade 2 stomatitis	Hold until stomatitis has resolved to \leq grade 1. Resume at one dose level below current dose level	Hold until recovery to \leq grade 1. Resume at the same dose level
Hypertension	Grade 3 Hypertension Or life threatening Hypertension	No dose modification necessary.	Withhold lenvatinib for Grade 3 hypertension that persists despite optimal antihypertensive therapy; resume at one dose level below current dose level. Discontinue for life threatening hypertension.
Cardiac dysfunction or Hemorrhage.	Grade 3 or Grade 4 events	No dose modification necessary	Withhold lenvatinib for development of Grade 3 event until improved to Grade 0 or 1 or baseline. Either resume at a reduced dose or discontinue lenvatinib depending on the severity and persistence of the adverse event.

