Proteinuria	>2 gms or less than 2 gms	No dose modification necessary.	Withhold lenvatinib for \leq 2 grams of proteinuria/24 hours. Resume at next dose level below current dose level; 2) when proteinuria is >2 gm/24 hours. Discontinue lenvatinib for nephrotic syndrome.
QTc Prolongation	Grade 3 or greater	No dose modification necessary	Monitor and correct electrolyte abnormalities in all patients. Withhold lenvatinib for the development of Grade 3 or greater QT interval prolongation. Resume lenvatinib at a one dose level below previous dose level when QT prolongation resolves to Grade 0 or 1 or baseline.

Day 8 dose of Eribulin may be delayed for a maximum of 1 week. If toxicities do not improve enough after 1 week delay then omit day 8 dose of Eribulin. If day 8 of Eribulin is omitted two consecutive cycles Eribulin should be resumed at one dose below current dose level.

Eribulin Dose Modifications

Starting dose and dose modifications for unacceptable toxicity that is thought to be related to Eribulin are listed below. Dose adjustments are to be made according to the greatest degree of toxicity. The most common toxic effects of Eribulin are fatigue, neutropenia (including neutropenic fever), peripheral neuropathy, and alopecia.

Eribulin Dose Modifications, TABLE 1

0	1.4
-1	1.1
-2	0.7

NOTE: Patients requiring a third dose reduction should be taken off study unless in the opinion of the investigator and/or the DSMB there is reason to believe that the patient is still experiencing clinical benefit (in such cases the DSMB will issue written approval).

Lenvatinib Dose Modifications

Recommended Dose Modifications for Persistent and Intolerable Grade 2 or Grade 3 Adverse Reactions or Grade 4 Laboratory Abnormalities, TABLE 2

0	20
-1	14
Note: Based on toxicity data of 1st 10 patients in Phase 2, starting Lenvatinib dose was not increased to 24 mg daily	

Other Toxicities with Lenvatinib

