7.2 Lenvatinib

Other names

Lenvima

Classification

LENVIMA, a kinase inhibitor, is the mesylate salt of lenvatinib. Its chemical name is 4-[3-chloro-4-(*N*¹-cyclopropylureido)phenoxy]-7-methoxyquinoline-6-carboxamidemethanesulfonate.

Mode of action

Lenvatinib is a receptor tyrosine kinase (RTK) inhibitor that inhibits the kinase activities of vascular endothelial growth factor (VEGF) receptors VEGFR1 (FLT1), VEGFR2 (KDR), and VEGFR3 (FLT4). Lenvatinib also inhibits other RTKs that have been implicated in pathogenic angiogenesis, tumor growth, and cancer progression in addition to their normal cellular functions, including fibroblast growth factor (FGF) receptors FGFR1, 2, 3, and 4; the platelet derived growth factor receptor alpha (PDGFR α), KIT, and RET.

Storage and Stability

Store at 25°C (77°F); excursions permitted to 15–30°C (59–86°F)

Protocol dose

Lenvatinib is administered at a dose of 20 mg orally.

Preparation

LENVIMA 4 mg capsules are supplied as hard hyperomellose capsules with yellowish-red body and yellowish-red cap, marked in black ink with “€” on the cap and “LENV 4 mg” on the body.

LENVIMA 10 mg capsules are supplied as hard hyperomellose capsules with yellow body and yellowish-red cap, marked in black ink with “€” on the cap and “LENV 10 mg” on the body.

Protocol administration

Lenvatinib is administered orally 20 mg po daily. It will be administered immediately after the Eribulin administration.

Incompatibilities

None

Availability

Lenvima will be supplied by Eisai, Inc in cards containing 10 mg and 4 mg capsules. To order drug, please contact EISAI IIS Department at [contact] or [contact]

Side effects

Detailed information regarding side effects and rates of adverse events of lenvatinib can be found in the package insert. Some of the most common side effects include:

Hypertension

The median time to onset of new or worsening hypertension was 16 days for LENVIMA-treated patients. The incidence of Grade 3 hypertension was 44% as compared to 4% for placebo, and the incidence of Grade 4 hypertension was less than 1% in LENVIMA-treated patients and none in the placebo group.

Cardiac dysfunction

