5.4 Hepatotoxicity

In Study 1, 4% of LENVIMA-treated patients experienced an increase in alanine aminotransferase (ALT) and 5% experienced an increase in aspartate aminotransferase (AST) that was Grade 3 or greater. No patients in the placebo group experienced Grade 3 or greater increases in ALT or AST. Across clinical studies in which 1108 patients received LENVIMA, hepatic failure (including fatal events) was reported in 3 patients and acute hepatitis was reported in 1 patient.

Monitor liver function before initiation of LENVIMA, then every 2 weeks for the first 2 months, and at least monthly thereafter during treatment. Withhold LENVIMA for the development of Grade 3 or greater liver impairment until resolved to Grade 0 to 1 or baseline. Either resume at a reduced dose or discontinue LENVIMA depending on the severity and persistence of hepatotoxicity. Discontinue LENVIMA for hepatic failure [*see Dosage and Administration (2.2)*].

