First occurrence	Interrupt until resolved to Grade 0-1 or baseline	20 mg (two 10 mg capsules) orally once daily
Second occurrence ^c	Interrupt until resolved to Grade 0-1 or baseline	14 mg (one 10 mg capsule plus one 4 mg capsule) orally once daily
Third occurrence ^c	Interrupt until resolved to Grade 0-1 or baseline	10 mg (one 10 mg capsule) orally once daily

^a Initiate medical management for nausea, vomiting, or diarrhea prior to interruption or dose reduction of LENVIMA

^b Reduce dose in succession based on the previous dose level (24 mg, 20 mg, or 14 mg per day)

^c Refers to the same or a different adverse reaction that requires dose modification

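### The lenvatinib liver rule in section 4.3 restarts at the starting dose after a first Grade 4 event, contradicts Table 2, and sets no hold at Grade 3

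*Combined protocol and SAP*

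**What the plan says.** The section 4.3 table is scoped to phase II patients after the DLT period. Its hepatic row has the trigger "Grade 4 AST, ALT or Total Bilirubin". The lenvatinib cell holds the drug until recovery to Grade 1 or baseline and then continues: "Resume at reduced dose of 20 mg po daily if first occurrence, reduce to 14 mg po daily on second occurrence", with 10 mg at the third occurrence. The eribulin cell of the same row uses a lower trigger: "If during treatment there is grade 3,4 liver toxicity then dose reduce by 1 dose level".

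Later in section 4.3, Table 2 is headed as applying to "Persistent and Intolerable Grade 2 or Grade 3 Adverse Reactions or Grade 4 Laboratory Abnormalities, TABLE 2". It lists level 0 as 20 mg and level -1 as 14 mg. Its note records that the "starting Lenvatinib dose was not increased to 24 mg daily". Section 7.2 agrees: "Lenvatinib is administered orally 20 mg po daily".

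Appendix I reproduces the lenvatinib label. Label section 5.4 says: "Withhold LENVIMA for the development of Grade 3 or greater liver impairment until resolved to Grade 0 to 1 or baseline". Label section 2.2 sets the same Grade 3 or 4 threshold. The label's own Table 1 steps through 20, 14 and 10 mg from a 24 mg start, and its footnote adds: "Reduce dose in succession based on the previous dose level (24 mg, 20 mg, or 14 mg per day)".

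On gastrointestinal perforation, the text under Other Toxicities with Lenvatinib in section 4.3 recommends stopping when the perforation is life-threatening. Label sections 5.7 and 2.2 stop the drug for any perforation and attach the life-threatening condition to fistula.

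**The concern.** A dose-modification table is what site staff use when a laboratory result comes back. For a first Grade 4 transaminase or bilirubin rise, this one gives two answers. The hepatic row puts the patient back on the dose at which the event occurred, and Table 2 takes the patient to 14 mg. In a multi-center trial, sites could follow either and both would be within protocol.

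The trigger matters separately. At Grade 3 the hepatic row reduces eribulin but does not hold lenvatinib, although the reproduced label withholds lenvatinib at that grade. Eligibility allows a Child Pugh score up to 10, and the row itself plans eribulin doses for known liver dysfunction, so liver events are a practical matter in this population. What is at stake is patient safety and consistent dosing across sites. The primary response test is not affected.

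**Working it through.** There is no sample-size or error-rate figure to reproduce here. The check sets the rules side by side and computes the dose steps.

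**Inputs.** Starting dose 20 mg (section 4.3, Table 2 level 0 and note; section 7.2). First restart dose in the hepatic row 20 mg. Table 2 level -1, 14 mg. Label steps 24, 20, 14 and 10 mg (Appendix I, label Table 1).

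**Step 1: size of the first cut.** Cut = (dose before - dose after) / dose before.

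| Rule | Dose before | Dose after | Cut |
|---|---|---|---|
| Hepatic row, first occurrence | 20 mg | 20 mg | (20-20)/20 = 0% |
| Table 2, level 0 to -1 | 20 mg | 14 mg | (20-14)/20 = 30% |
| Label, step down from 20 mg | 20 mg | 14 mg | (20-14)/20 = 30% |
| Label, own first step from 24 mg | 24 mg | 20 mg | (24-20)/24 = 16.7% |

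The hepatic row and Table 2 differ by 20-14 = 6 mg a day for the same event.

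**Step 2: likely source.** The row's 20/14/10 mg sequence is the label's sequence for a 24 mg start. The label footnote steps down from the previous dose, so a patient starting at 20 mg would go to 14 mg. The hypertension and QTc rows of the same table already use relative wording, one level below the current dose. The liver row therefore looks like text left over from the 24 mg option. That is an inference; the documents do not state it.

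**Step 3: trigger grade.**

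| Source | Grade at which action on the drug starts |
|---|---|
| Hepatic row, lenvatinib | 4 |
| Hepatic row, eribulin | 3 |
| Label 5.4 and 2.2, lenvatinib | 3 |

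Table 2 does not close this gap. It reaches laboratory abnormalities only at Grade 4, and Grade 3 adverse reactions only when they are both persistent and intolerable. A Grade 3 enzyme rise without symptoms is not clearly covered.

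**Step 4: perforation.** Section 4.3 applies the life-threatening condition to perforation; the label applies it only to fistula. A perforation not judged life-threatening is therefore outside the section 4.3 recommendation but inside the label's stop rule. How far the condition reaches to fistula in the section 4.3 sentence is ambiguous, and nothing is claimed about it.

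**Step 5: which text governs.** Section 12.0 requires conduct as the approved protocol describes, but the hepatic row, Table 2 and Appendix I are all in that protocol. No sentence was found that ranks them.

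**The case against.** The strongest reply is that a protocol need not copy a label. The reproduced label is for single-agent lenvatinib at 24 mg in thyroid cancer; this trial gives 20 mg with eribulin in other tumors and may set its own rules. That stands as a principle: a difference from the label is not in itself an error. But section 4.3 largely paraphrases the label and states no intended departure, and the principle cannot explain a reduction from 20 mg to 20 mg or the conflict with Table 2.

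A second reply is that the synopsis and sections 4.1 and 8.1.1 still carry a 24 mg option, under which 20 mg would be a true reduction. The Table 2 note closes that option.

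A third is that other safeguards exist. In cycle 1, drug-related non-hematologic toxicity of Grade 3 or above is generally dose-limiting (Appendix III). Section 4.2 requires laboratory tests before dosing, and section 4.7 allows stopping for unacceptable toxicity or at the physician's discretion. These reduce the risk. They do not say when to hold lenvatinib for a liver event or at what dose to restart.

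Two stronger readings are tempting and are not supported.

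- A reader might infer that every patient with a first Grade 4 liver event would restart at 20 mg. That holds only if the row is read apart from Table 2. What the text shows is two conflicting instructions.
- A reader might infer that the label's stops for Grade 4 cardiac events or hemorrhage, hepatic failure and arterial thrombotic events, and its renal hold, are missing from the protocol. They are in Appendix I, which is part of it, and nothing in section 4.3 contradicts them. The cardiac and hemorrhage row's choice between resuming at a lower dose and stopping is not limited to Grade 3 either.

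**Conclusion.** The lenvatinib cell of the hepatic row is wrong as written and should be corrected. Its first restart dose is a 0% cut where Table 2, in the same section, gives 30%. Its Grade 4 trigger is one grade looser than both the eribulin cell beside it and the reproduced label. The perforation sentence is a secondary point that needs clarifying.

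This rests on two assumptions: that the Table 2 note is the final decision on the starting dose, and that the table cells are read in the columns where they appear. It applies to phase II patients after the DLT period. No number of affected patients is estimated. The label gives rates for Grade 3 or greater enzyme rises with single-agent 24 mg (4% for ALT, 5% for AST), but the documents give no rate for the disputed grades in this combination.

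**What to change.** **Hepatic row, lenvatinib cell.** Trigger at Grade 3 or 4 AST, ALT or total bilirubin. Hold until Grade 0-1 or baseline. Restart at 14 mg after the first occurrence and at 10 mg after the second. Stop at the third occurrence, or at any time for hepatic failure.

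**Table 2.** Add level -2 = 10 mg. Without it, an instruction to go one level down has nowhere to go from 14 mg, and the row's existing 10 mg step would be lost. The steps are then (20-14)/20 = 30% and (14-10)/14 = 28.6%. For Grade 4 events, stopping at the third occurrence also agrees with section 4.7, which ends therapy for Grade 4 toxicity after two dose modifications.

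**Other Toxicities with Lenvatinib, section 4.3.** State that lenvatinib is stopped for any gastrointestinal perforation, and for a fistula that is life-threatening.

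**Optional.** Repeat the label's Grade 4 stop in the cardiac and hemorrhage row, as a clarification only.

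A general sentence that the more protective rule always applies is not recommended. It would leave sites to judge case by case, and it would override the rows that resume lenvatinib at the same dose after nausea, vomiting or stomatitis.

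The cost is one table cell, one added dose level and one sentence, with slightly more lenvatinib holds, reductions or stops. Sample size and the primary analysis are unchanged.

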4.3 Supportive Care Guidelines

Supportive therapy for neutropenia:

If grade 3 or 4 neutropenia develops (ANC<1000/uL), G-CSF (Neupogen) can be administered, at the discretion of the treating investigator, until resolution of neutropenia. Neulasta (PEG-filgrastim) 6mg SC for 1 dose is recommended. If Neulasta is given, chemotherapy cannot be administered within 14 days. Neupogen can also be given at the discretion of the treating investigator. NOTE: Neupogen can be given any time before or after chemo. HOWEVER, Neulasta cannot be given within 14 days of chemotherapy.

Supportive therapy for neuropathy

Gabapentin or similar medications can be given at the discretion of the treating physician per institutional practice.

Dose Delays & Dose Modifications

Toxicities will be graded using NCI CTCAE version 4.03 (see Appendices). Dose delays and modification of lenvatinib and Eribulin are summarized below (for post-DLT period in phase II patients only). Individual patient dose reductions are also provided in separate tables.

Dose Delay & Modification for Eribulin and Lenvatinib

Toxicity	Adverse event	Dose Reduction/Delay	
		Eribulin	Lenvatinib
Hematologic toxicity attributed to any or all treatment	Platelets 75000-99999/mm ³ within 24 hrs prior to scheduled therapy	If Day 1: Hold until recovery of platelets >100,000/mm ³ . Resume at the same level after recovery If Day 8: No intervention	No dose modification necessary
	ANC <1000/mm ³ or Platelets 25000-74999/mm ³ within 24 hrs prior to scheduled therapy	If Day 1: Hold until recovery to ANC >1000/mm ³ and Platelets 100000/mm ³ . Resume at same level after recovery If Day 8: Hold until recovery to ANC >1000/mm ³ and Platelets 75000/mm ³ . Resume at same level after recovery	Hold until recovery to ANC >500/mm ³ and platelets more than 25000, Resume at same level after recovery.
	Platelets <25000/mm ³ or Platelets 25000-50000/mm ³ complicated by bleeding, easy bruising, petechiae, or requiring platelet transfusion	If Day 1: Hold until recovery to Platelets 100000/mm ³ . Resume at same level after recovery If Day 8: Hold until recovery to Platelets 75000/mm ³ . Resume at same level after recovery	Hold until recovery of Platelets 25000/mm ³ . Resume at current dose level.

	Prolonged neutropenia (ANC<500/mm ³ for >7 days)	Hold until recovery to ANC>1000/mm ³ . Resume at one dose level below current dose level	Hold until recovery to ANC>500/mm ³ . Resume at same level dose.

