8.0 Statistical Considerations

8.1 Proposed sample size

8.1.1 Safety run in phase

The number of subjects in the safety run-in phase will be 10. In the phase II trial the number of patients will be 30. Three patients will receive lenvatinib at 20 mg qd and Eribulin at 1.4 mg/m² day 1 and day 8 of a 21 day cycle. Eribulin will be given on day 1 and lenvatinib will be started on day 2. If no DLTs are experienced, then the Phase II trial will be initiated at a dose of 24 mg daily of lenvatinib and Eribulin at 1.4 mg/m² day 1 and day 8 of a 21 day cycle. If there is a DLT, then three more patients will be treated at that dose level. If no more DLTs are observed, then the phase II trial can commence at lenvatinib dose of 20 mg qd and Eribulin at 1.4 mg/m² day one and day 8 of a 21 day cycle. If there is another DLT, then there will be a dose reduction of lenvatinib to 14 mg daily.

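### The hepatic-toxicity row restarts lenvatinib at a 'reduced' 20 mg, which is the trial's starting dose, so a first Grade 4 liver event brings no lenvatinib reduction and the row conflicts with Table 2

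*Combined protocol and SAP*

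**What the plan says.** The dose delay and modification table in section 4.3 has a hepatic row triggered by Grade 4 AST, ALT or bilirubin. Lenvatinib is held until the abnormality is back to Grade 1 or baseline. The cell then continues: "Resume at reduced dose of 20 mg po daily if first occurrence", and after that "reduce to 14 mg po daily on second occurrence and 10 mg po daily on third occurrence". The eribulin cell of the same row adds: "If during treatment there is grade 3,4 liver toxicity then dose reduce by 1 dose level". The table is said to apply "for post-DLT period in phase II patients only".

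The dose patients actually start on is given elsewhere. Section 4.1 puts the first ten patients on 20 mg daily, and section 7.2 states: "Lenvatinib is administered at a dose of 20 mg orally". Table 2 in section 4.3 sets level 0 at 20 mg and level -1 at 14 mg. Its title extends to Grade 4 laboratory abnormalities, and its note records, from the toxicity seen in the first ten patients, that the "starting Lenvatinib dose was not increased to 24 mg daily".

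Other parts of the table use relative wording. "Resume at one dose level below current dose level" is the instruction for eribulin after prolonged neutropenia, for example. The lenvatinib cells for persistent Grade 3 hypertension and for QTc prolongation are written in the same relative way.

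**The concern.** A dose described as reduced should be lower than the dose the patient was taking. Here it is the same dose. Grade 4 liver enzymes or bilirubin are laboratory abnormalities, so the hepatic row and Table 2 both cover the event and give different restart doses: 20 mg and 14 mg. Section 4.3 does not say which prevails. A site that follows the event-specific row would put the patient back on the full starting dose after a Grade 4 liver event and could believe that a reduction had been made.

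The row also counts hepatic occurrences and ignores the dose being taken. A patient already lowered to 14 mg for another toxicity therefore finds no usable reduced dose in it at a first liver event.

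**Working it through.** **Inputs.** Starting dose 20 mg (sections 4.1 and 7.2; Table 2 level 0 and note). Table 2 level -1: 14 mg. Hepatic row: 20, 14 and 10 mg for first, second and third occurrence. Appended label (Appendix I, sections 2.1 and 2.2): recommended dose 24 mg, then 20, 14 and 10 mg, with footnotes that reductions go in succession from the previous dose and that an occurrence may be the same or a different reaction. Eribulin levels (section 4.3, Table 1): 1.4, 1.1 and 0.7 mg/m².

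**Where the sequence comes from.** The row's three doses match the label's Table 1 exactly. They form three true reductions only from 24 mg. Change = (restart dose - current dose) / current dose:

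| Dose at start | First event | Second event | Third event |
|---|---|---|---|
| 24 mg (label) | 24 to 20: -4/24 = -17% | 20 to 14: -6/20 = -30% | 14 to 10: -4/14 = -29% |
| 20 mg (this trial) | 20 to 20: 0/20 = 0% | 20 to 14: -30% | 14 to 10: -29% |

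**What the trial's own levels give.** From level 0, one level down is 20 to 14 mg: 1 - 14/20 = 30%. The row and Table 2 therefore differ by 20/14 = 1.43 at the first event. If exposure is proportional to dose, as label section 12.3 reports for 3.2 to 32 mg, exposure under the row would also be about 43% higher. That is the same contrast in other units, not a second effect.

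**A patient already at 14 mg at a first liver event** (for example, after persistent Grade 3 hypertension):
- Counting liver events only, the row names 20 mg, which cannot be a reduced dose.
- Counting any reaction, as the label does, this is the second occurrence and the row names 14 mg: no change.
- Stepping down from the previous dose, as the label's footnote requires, gives 10 mg: 1 - 10/14 = 29% reduction. The row carries neither label footnote.

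**What else happens at the same event.** Eribulin drops one level, from 1.4 to 1.1 mg/m²: 1 - 1.1/1.4 = 21%.

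**The case against.** The best defence is that the right step is already in the protocol. Table 2 covers this event, gives 14 mg and carries the note about 24 mg. On that view the row is a leftover from the period when a 24 mg phase II dose was possible (the synopsis and sections 4.1 and 8.1.1 still describe that option), and it would be correct for such a dose. This explains the error but does not remove it. The two instructions still conflict, no precedence is stated, and the one written for liver events is the wrong one.

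The consequences are also limited, and that stands. Lenvatinib is held until recovery, eribulin is lowered, the physician may stop treatment (section 4.7), and the table applies only after the DLT period in phase II. The eribulin step is not available to everyone: a patient with known liver dysfunction and Child Pugh B starts at 0.7 mg/m², the lowest listed level, although the exclusion of significant non-neoplastic liver disease should make such patients few.

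Two stronger readings are tempting, but the documents do not support them.
- A reader might infer that a patient at 14 mg must be raised to 20 mg, a 43% increase (6/14). The row's own word for the restart dose, reduced, rules that out. What remains is that the row gives this patient no clear dose.
- A reader might infer that a third Grade 4 liver event could be reached after only one lenvatinib reduction (20, 20, 14 mg), with the patient still on therapy. Section 4.7 removes a patient for Grade 4 toxicity after two dose modifications and does not restrict these to lenvatinib. The hepatic row itself lowers eribulin at each such event, and 1.4 to 1.1 to 0.7 mg/m² is already two.

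Section 8.1.1 ("If there is another DLT, then there will be a dose reduction of lenvatinib to 14 mg daily") agrees that 14 mg lies below 20 mg. It is a run-in rule for the trial dose, however, and not a restart rule for an individual, so it is only weak support.

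**Conclusion.** Wrong as written, and it should be corrected. At the first Grade 4 liver event the row gives a 0% lenvatinib reduction where Table 2 gives 30%. The harm depends on a site following the row and not Table 2, which the protocol leaves open. The finding rests on the 20 mg start, which Table 2 and section 7.2 both state. It does not depend on whether Table 2 has any line below 14 mg.

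Few patients should be affected. The label reports Grade 3 or greater ALT in 4% and AST in 5% of patients on 24 mg monotherapy. The documents give neither a Grade 4 rate nor a rate for the combination, so no expected number among the 30 patients can be stated. There is no effect on the response-rate decision or power.

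**What to change.** Reword the lenvatinib cell of the hepatic row, for example: *Keep lenvatinib on hold until the abnormality is back to Grade 1 or baseline; then restart one step below the dose taken at the time of the event (20 to 14 mg, 14 to 10 mg), or stop permanently, depending on its severity and persistence.* Later Grade 4 events then fall under the existing off-therapy rule in section 4.7, so no new stopping rule is needed.

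Keep the 10 mg step inside the hepatic row, where it already appears, and leave Table 2 unchanged. Adding a 10 mg level there would also extend the hypertension, proteinuria and QTc rules, which step down by dose level. That would be a separate change of dosing policy.

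The cost is one reworded cell in a protocol amendment. The 10 mg and 4 mg capsules are already supplied (section 7.2), and no patients, visits or analyses are added.

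### After a first grade 4 liver event, the section 4.3 hepatic row restarts lenvatinib at 20 mg, which is this trial's full dose and no reduction

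*Combined protocol and SAP*

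**What the plan says.** The dose table in section 4.3 is introduced as applying "for post-DLT period in phase II patients only". Its hepatic row is triggered by "Grade 4 AST, ALT or Total Bilirubin". The lenvatinib cell of that row has the drug held until recovery, and then: "Resume at reduced dose of 20 mg po daily if first occurrence", with later steps "reduce to 14 mg po daily on second occurrence and 10 mg po daily on third occurrence". The eribulin cell of the same row says: "If during treatment there is grade 3,4 liver toxicity then dose reduce by 1 dose level".

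The trial's lenvatinib dose is 20 mg daily in section 4.1 (run-in) and section 7.2 (protocol dose). Table 2, at the end of section 4.3, lists level 0 as 20 mg and level -1 as 14 mg, and nothing lower. Its title includes grade 4 laboratory abnormalities. A note in it states that, on the toxicity seen in the first 10 patients, the starting dose was not raised to 24 mg.

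Other rows of the same table express a lenvatinib reduction relative to the patient's dose:
- Hypertension: "Withhold lenvatinib for Grade 3 hypertension that persists despite optimal antihypertensive therapy; resume at one dose level below current dose level".
- QTc prolongation: "Resume lenvatinib at a one dose level below previous dose level when QT prolongation resolves to Grade 0 or 1 or baseline".
- Proteinuria, for the dose step only: "Resume at next dose level below current dose level".

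**The concern.** The cell promises a reduction and prints the full dose. A site that follows it re-exposes a patient recovering from grade 4 liver toxicity to lenvatinib at the dose on which the event occurred. A site that gives 14 mg follows Table 2 but departs from the row written for this toxicity. Section 12.0 expects the study to be run exactly as the protocol describes outside emergencies, so either choice departs from some part of section 4.3.

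The fixed doses cause a second problem. Occurrences in this row are counted within liver events, so a patient already on 14 mg because of hypertension or QTc prolongation would be told to resume at 20 mg after a first liver event.

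Patient safety and consistent dosing across sites are at stake. The primary analysis is not.

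**Working it through.** **Inputs**
- Hepatic row, lenvatinib: 20 mg on the first occurrence, 14 mg on the second, 10 mg on the third (section 4.3).
- Trial dose: 20 mg (sections 4.1 and 7.2; Table 2 level 0 and its note).
- Table 2 level -1: 14 mg.
- Appended label (Appendix I, label sections 2.1 and 2.2): recommended dose 24 mg. Label Table 1 steps to 20, 14 and 10 mg, and its footnote b has each cut taken from the dose the patient was on before.
- Eribulin levels: 1.4, 1.1 and 0.7 mg/m² (Table 1 of section 4.3).

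**Where 20 mg is a reduction.** Cut = (old dose − new dose) / old dose. From the label's start: (24 − 20) / 24 = 16.7%. The row describes a true reduction only for a patient on 24 mg.

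**The row applied to this trial's 20 mg dose**
- First occurrence: (20 − 20) / 20 = 0%.
- Second: (20 − 14) / 20 = 30%.
- Third: (20 − 10) / 20 = 50%, at a dose that Table 2 does not list.

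**Table 2 applied to the same first event.** (20 − 14) / 20 = 30%. Label footnote b also gives 14 mg from 20 mg.

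**Size of the gap at restart**
- Ratio: 20 / 14 = 1.43.
- Per 21-day cycle: 20 × 21 = 420 mg against 14 × 21 = 294 mg, a difference of 126 mg.

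**Patient already on 14 mg.** Literal row: (20 − 14) / 14 = +43%.

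**Eribulin in the same row.** From 1.4 to 1.1 mg/m²: (1.4 − 1.1) / 1.4 = 21%. Eribulin does come down after the event; lenvatinib does not.

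**Comparison rows.** None of these rows prints 14 mg. The hypertension and QTc rows call for one level lower, which through Table 2 is 14 mg for a patient on 20 mg. The hypertension row applies only when grade 3 persists despite optimal treatment. The proteinuria row has the same dose step, but its thresholds are reversed: it withholds at or below 2 g and resumes above 2 g per 24 hours. Footnote 11 of section 6.0 and label section 5.5 say the opposite.

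**Effect on the design.** The exact rule in section 8.1.2 reproduces. With n = 30 and success at 10 or more responses, P(X ≥ 10 | p = 0.2) = 0.0611 and P(X ≥ 10 | p = 0.4) = 0.8237. Neither figure uses the dose table.

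**The case against.** The strongest reply is that an investigator will see that a reduction was meant and will turn to Table 2. The hold until recovery, the eribulin cut and the physician's right in section 4.7 to stop therapy add protection. These safeguards are real, but none of them changes the lenvatinib dose printed in the row, and no text says that Table 2 overrides it. Section 4.3 says only that individual reductions also appear in separate tables.

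A second reply is that the synopsis and sections 4.1 and 8.1.1 still describe a possible rise to 24 mg, from which 20 mg would be a genuine step down. The note in Table 2 answers that: the rise was not made.

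A third reply is that restarting lenvatinib at the same dose is not unusual in this table. That is correct. The rows for low platelets, prolonged neutropenia, febrile neutropenia, nausea/vomiting and stomatitis all do so, and three of them (prolonged neutropenia, febrile neutropenia and stomatitis) cut eribulin alone. A reader might therefore infer that the hepatic row is the one place where lenvatinib is left at full dose, and the documents do not support that. What sets this row apart is that it states a reduction and gives none, against a table whose title covers the event.

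A reader might also infer that the 10 mg step conflicts with the stopping rule in section 4.7. That depends on how dose modifications are counted across drugs and steps, which section 4.7 does not define, so the conflict cannot be asserted.

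**Conclusion.** Wrong as written. For a patient on 20 mg with a first grade 4 AST, ALT or bilirubin event after the DLT period, the row gives a 0% lenvatinib cut where Table 2 gives 30%. For a patient already on 14 mg, its literal reading raises the dose by 43%. The conclusion rests on taking the Table 2 note as the current position on starting dose, and on reading the row as printed.

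A reader might want a count of patients affected, but the documents do not support one. Section 7.2 gives grade 3 or greater ALT and AST rises of 4% and 5% with lenvatinib alone. The grade 4 share, bilirubin events and the rate with eribulin are not stated. Nor should the point be read as touching the trial's statistical conclusion: sample size, alpha, power and the 10-of-30 rule are unaffected.

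**What to change.** In the lenvatinib cell of the hepatic row, keep the existing hold and replace the three fixed doses with a relative instruction: after recovery, restart one Table 2 level under the dose the patient was taking, with 20 mg to 14 mg given as the worked case. This also covers a patient already lowered for another toxicity. The hypertension and QTc rows can serve as models for the dose step. The proteinuria row should not be copied while its thresholds are reversed.

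For a further event at 14 mg, the sponsor should choose one of two rules and state it: discontinue lenvatinib, or add 10 mg to Table 2 as level -2 and restart there. Either makes the row and the table agree.

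The cost is a wording amendment to one cell, one extra line in Table 2 if 10 mg is kept, and a notice to sites. No patients, visits or data are added.
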